5.3.2.3. Assessment of parents who receive false negative results

Parents who have received false negative results will not be definitively identified until the 12 month follow-up stage of the project. So, although some may have been included in

the sample of parents receiving negative results, the main assessment of these parents will occur at that stage and no formal comparison with their immediate post-testing perceptions will be possible within the time-frame and scope of the project.

5.3.2.4. Assessment of acceptability to health professionals

The acceptability of PO as a routine procedure to health professionals will be addressed by holding focus groups with midwives, midwifery assistants and other staff who carry out the test (for example nursery nurses and health care assistants) at Birmingham Women's Hospital and one of the other study centres after they have had experience of this (see Appendix H for information sheet). Issues to be explored will include perceptions of the efficacy of testing, costs to staff in terms of time and effort involved, perceived benefits of testing, professional views on the impact on parents. The discussions of the focus groups will be recorded, transcribed and analysed using inductive thematic analysis.

To address the acceptability of PO to neonatologists, echocardiographers, registrars and senior house officers (SHOs), staff at all study centres will be invited to complete open-ended questionnaires administered by e-mail (see Appendix G for information sheet). Focus groups for these groups would not be feasible because of the rotation of posts for registrars and SHOs. Issues to be explored will be similar to those addressed in the focus groups (see Appendix F for questionnaire; precise wording/details may be amended following further discussion with professionals and piloting). In order to allow participants to respond to the thoughts of their peers, an anonymised summary of responses will be compiled and emailed to participants, with the invitation to add further thoughts. Participants will not be identifiable to each other; all participants will reply to the researcher and not to each other. Responses will be analysed using inductive thematic analysis.

5.4. Additional information sought

In addition to the PO and clinical examination information, a minimal demographic and clinical dataset will be collected (see Appendix D). Some additional data will be collected postnatally. This will include baby birth weight and mother ethnicity. If there was an antenatal diagnosis or suspicion of CHD, limited information on the ultrasound findings will be extracted from the maternity notes. The baby's NHS number will be used as the primary identifier. All babies are issued with unique NHS numbers and these are used to track individuals throughout the NHS, making it a safe identifier. Addresses will not be collected on all mothers for the purposes of the study, to reduce the amount of identifiable data transferred out of the hospital. Addresses and telephone numbers will be collected for only a small sample of mothers for the administration of the acceptability questionnaires (see section 5.3.2)

5.5. Health economic outcomes

5.5.1 Perspective and cost data collection

If PO screening is shown to be an effective adjunct to the standard practice of use of clinical examination to screen for CHD in newborn babies, then it is likely that important cost implications will be seen for the health care sector. For example, PO may detect additional cases of abnormality compared to standard clinical examination alone which increase the number of echocardiograms required and increase the number of cases of infants requiring cardiac surgery (i.e. babies that could have had surgery but died before this was possible). But the additional associated costs of early diagnosis and treatment may lead to a reduction in costs associated with undetected CHD and avoided complications. Given this, the economic evaluation will take the perspective of the NHS.

Resource use data will be collected to estimate the costs associated with the additional use of PO in screening newborn babies. Data on NHS resource use will be prospectively collect for a sub-sample of the study. The main resources to be monitored include:

1. the additional time for the procedure of PO screening and consultation/explanation, compared to current practice, during pregnancy (principally midwife and paediatrician time),
2. the equipment and resources associated with PO and knock-on costs associated with additional echocardiograms,
3. time and resources associated with clinical examination
4. neonatal cardiac surgery
5. admissions to neonatal intensive care.

Information on unit costs or prices will then be required to attach to each resource item in order that an overall cost per infant can be calculated. Cost data will be collected from two principal sources. First, the primary PO test accuracy study will provide the time (staff and equipment) and other resource use data to estimate cost incurred in administering the PO test and the knock on tests. Primary cost data for many of these resources will be collected from the participating hospital sites. Where possible other cost data, such as cost of midwife time etc to carry out the test will be collected from routine sources, including Netten *et al* (34) and hospital finance departments. Many cost data are already available in recently published sources. A study to investigate the costs of different levels of neonatal intensive care has already been carried out (35) and other cost studies with relevant costs and costs associated with pre term delivery are available to supplement these (36;37). Also recent systematic review and cost-effectiveness analysis on Newborn Screening For Congenital Heart Defects has been recently published (6). This study retrieved available literature costs and some primary costs which can be used as a comparison.

5.6. Data management and validation

5.6.1 Confidentiality of personal data

The study will collect personal data and sensitive information about the participating infants. Participants will be informed about the transfer of this information to the Pulse Ox study office at the University of Birmingham Clinical Trials Unit (BCTU) and will be asked to consent to this. Participant demographic data, test results and questionnaire answers will be stored on a secure server, inputted where possible via the internet using secure socket layer encryption technology. Remaining data will be returned by post to the BCTU. The use of the baby's NHS number will minimise the risk of disclosure of identifiable data. Data to be processed outside the BCTU, or cross-referenced with CARs, will be anonymised. Only registered study personnel will have access to the database.

All participant data will be processed and stored according to the MRC guidelines of use of personal data. All personal information obtained for the study will be held securely and treated as confidential. All staff, at the hospitals, in the community midwife teams or at the BCTU, share the same duty of care to prevent unauthorised disclosure of personal information. No data that could be used to identify an individual will be published.

5.6.2 Long-term storage of data

All participant data will be stored on computer for 20 years after recruitment in accordance with MRC guidelines on the archiving of personal medical data for research.

6. ACCRUAL AND ANALYSIS

6.1. Sample size

The approach used in the sample size calculations is to consider the power that a study of a certain size has for the lower limits of the confidence intervals for both sensitivity and specificity to exceed particular values (and hence prove that the test is statistically significantly superior to those values). Sample size computations have been undertaken assuming that the screening strategy will have a sensitivity of 75% and a specificity of 99.5%. Sample sizes for CHD prevalence between 2 and 5 per 1000 using a one-tailed significance level of 2.5% have been computed.

Simulations of the study design and analysis (using 10,000 repetitions) were performed to account for (1) sampling variability in the observed number of cases of CHD and (2) sampling variability in the observed sensitivity and specificity, and (3) to incorporate the use of binomial exact methods to estimate confidence intervals. Standard asymptotic sample size computations do not allow for all three of these issues to be considered simultaneously. Plots of power against the values of sensitivity and specificity that the study wishes to rule out were constructed for sample sizes of 10000, 15000, 20000, 25000, 30000 and 35000.

Based on these simulations it was observed that a sample size of 20,000 will have 80% power to demonstrate that sensitivity is above 61% at a prevalence of 5 per 1000 in the overall sample. For the subgroup of women who are not selectively screened antenatally, it is anticipated the prevalence to be around 2 per 1000, a level at which sensitivity of 52% can be detected with 80% power. If the sample size is increased to 25,000 the study will have 80% power to prove the sensitivity to be above 63% and 55% at 5 and 2 per 1000 CHD prevalences respectively; if it is increased to 30,000 the corresponding values are 64% and 57%. Variation of prevalence does not affect the power to detect differences in specificity. For sample sizes above 15,000 the study will have greater than 90% power to prove that the specificity is above 99.3%.

Further simulations using lower assumed values of the sensitivity and specificity for the screening strategy were undertaken. Statistical power to test absolute differences in sensitivity and specificity of the same magnitude was noted to be comparable to the above scenario for assumed values are within a reasonable range of those used above. Thus a sample size of 25,000 will have 80% power to prove that sensitivity is higher than a value 12% (prevalence 5 per 1000) or 20% (prevalence of 2 per 1000) below the assumed sensitivity of the test, and the specificity is above a value 0.2% below the assumed specificity.

The assumption about disease prevalence is quite conservative. A review of 62 prevalence studies since 1955 estimated a combined prevalence of 6 per 1000 live births of moderate to severe CHD (38). If prevalence in this study is higher than 0.5%, it will have more than the projected power to undertake subgroup analyses confidently. On this basis, considering the likely prevalence, the study aims to recruit a sample of 20,000 neonates.

6.2. Projected accrual and attrition rates

Accrual and attrition rates will be closely monitored against our target, and in the unlikely event that recruitment is insufficient, the Study Management Group have identified other maternity units likely to be able to participate.

6.3. Analysis for test accuracy study

The main analysis for diagnostic accuracy will include estimation of sensitivity, specificity, predictive values, likelihood ratios and their 95% confidence intervals. The baseline

characteristics of the patients enrolled in the study will be examined and planned subgroup analyses will be undertaken. Subgroup analyses are limited by statistical power and can produce spurious results particularly if many are undertaken. The recent literature review and consultation with obstetricians suggests that the accuracy of the index tests may vary according to risk factors (high risk history or antenatal suspicion on ultrasound) and timing of PO test. Therefore, secondary analyses will be limited to these subgroups only. The main and subgroup analyses are powered as outlined above based on conservative prevalence estimates. All estimates of accuracy for subgroups will be interpreted with appropriate caution.

As secondary analyses, the reference standard information obtained from echocardiography will be utilised to compare antenatal screening with PO. Such studies are commonplace in cancer research where invasive tests cannot be undertaken on those with low probability of disease. From such a design, it is possible to estimate the relative true (TPR) and false (FPR) positive rates of the two test strategies, but not the absolute sensitivity or specificity of either(39). It is also possible to estimate the trade-off between additional true positives and false positives related to the addition of PO to the standard screening programme (40). The statistical significance of the difference will be assessed using McNemar's test for paired data, and confidence intervals for the ratios computed using the methods of Cheng and Macalouso (41). The same approach can be utilised for comparing PO and clinical examination except that this analysis will be biased due to lack of blinding between the two tests. A "latent class" analysis, as described by Walter (42), will be used to estimate the sensitivity and specificity of the PO test and the antenatal screening from the screen positive study using only echocardiography as a reference standard. This approach involves an assumption of independence of test errors in the diseased and non-diseased groups, which will be tested as part of the investigation.

Using multivariable logistic regression analysis, predictive probabilities will be generated for various combinations of history, antenatal tests and oximetry results (43) Historical features to be included in the regression model will include gestational age (35-37, >37 weeks' gestation), antenatal scan findings, clinical examination (although this is likely to be affected by workup bias) and family history of CHD. In statistical terms, logistic modelling will aim to derive a diagnostic regression function, i.e. probability of CHD given test result. The analysis will be performed with presence or absence of CHD verified by reference standard as the binary dependent (outcome) variable. The models will allow a direct estimation of the post-test-combination disease probabilities that is needed for decision-making and for decision-analysis. Models of varying complexity may be compared through the familiar receiver operating characteristic (ROC) analyses. More importantly, the clinical situation where some information is already acquired, such as antenatal ultrasound or presentation with symptoms prior to undertaking PO, will be mirrored. In this way, for various index test results conditional disease probabilities will be generated directly taking into account any overlap of information that may exist between tests. This approach evaluates the extent to which the findings of the index tests add value to the babies' presentation. Its output is transparent, and is likely to enable production of simple clinical algorithms based on probabilities. The advantages of tackling diagnostic problems with logistic regression modelling are well known (44;45). The limitation associated with the regression approach lies mainly in its generalisability to other data sets or clinical practices. The recommended techniques, such as bootstrapping to enhance generalisability and estimate the amount of shrinkage will be applied for model validation (46;47). It is anticipated that the sample will comfortably meet the recommended events per variable rule to avoid overfitting the models (48-50) even if some data were missing. In a sensitivity analysis, missing data will be estimated by multiple imputation and maximum-

likelihood methods, as appropriate, to explore the potential bias and reduced statistical power associated with listwise deletion (51).

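### Section 6.3 says the subgroup analyses are powered, but section 6.1 gives no power for timing or high-risk subgroups, and its one subgroup figure uses the whole 20,000 as the denominator

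*Protocol*

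**What the plan says.** Section 6.1 sets the criterion: the lower confidence limit for sensitivity must exceed a stated value. It assumes a true sensitivity of 75% and a one-sided 2.5% level. For the whole study it states that "a sample size of 20,000 will have 80% power to demonstrate that sensitivity is above 61% at a prevalence of 5 per 1000". It then turns to one subgroup: "For the subgroup of women who are not selectively screened antenatally, it is anticipated the prevalence to be around 2 per 1000", at which prevalence it gives 80% power against 52%. It repeats the pair for 25,000 (63% and 55%) and 30,000 (64% and 57%), and fixes the recruitment target at 20,000. It gives neither the size nor the share of that subgroup. It adds that, if prevalence exceeds 0.5%, "it will have more than the projected power to undertake subgroup analyses confidently".

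Section 6.3 limits the secondary analyses to two factors: risk (high-risk history or antenatal suspicion on ultrasound) and timing of the test. It then states: "The main and subgroup analyses are powered as outlined above based on conservative prevalence estimates". The same paragraph also warns that subgroup analyses have limited power, and says their estimates will be read with caution.

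**The concern.** The sentence in 6.3 refers back to 6.1 for a design property that 6.1 does not supply. Nothing there concerns timing, and on the risk factor only the low-risk side has a figure. That figure also appears to use the total sample size as the size of a part of it.

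These analyses carry weight in the protocol. Section 2.2 presents the spread of test times as allowing analysis of the best time to screen. Section 3.1.3 treats the antenatally suspected group as important input to the decision model. A reader who relies on the sentence could take an imprecise timing estimate, or an absence of visible variation with timing, as an adequately powered result.

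**Working it through.** **Inputs (section 6.1).** True sensitivity 75%; one-sided 2.5%; simulations that allow for "sampling variability in the observed number of cases of CHD" and "incorporate the use of binomial exact methods to estimate confidence intervals"; prevalence 5 per 1000 overall and 2 per 1000 in the low-risk subgroup; N = 20,000.

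**Formula.** With N babies, prevalence π and a sensitivity p0 to be excluded,

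power = Σₙ P(n cases | N, π) × P(X ≥ cₙ | n, 0.75),

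where both distributions are binomial and cₙ is the smallest x with P(X ≥ x | n, p0) < 0.025. This is the same as the exact lower limit exceeding p0.

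**Step 1: reproduce the printed figures, using the full N each time.**

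| N | Prevalence | Value excluded | Power |
|---|---|---|---|
| 20,000 | 5/1000 | 61% | 82.5% |
| 25,000 | 5/1000 | 63% | 79.7% |
| 30,000 | 5/1000 | 64% | 80.7% |
| 20,000 | 2/1000 | 52% | 80.8% |
| 25,000 | 2/1000 | 55% | 80.3% |
| 30,000 | 2/1000 | 57% | 79.7% |

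The 82.5% is a rounding effect: at N = 20,000 and 5 per 1000, 80% power is reached at 61.4%, which rounds to 61%. The method is therefore the protocol's, and the three low-risk figures were obtained with the subgroup equal to the whole study.

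**Step 2: consistency.** Overall cases are 20,000 × 0.005 = 100. If all 20,000 were low-risk, cases would be 20,000 × 0.002 = 40 and overall prevalence would be 2 per 1000. The two statements cannot both describe one sample of 20,000.

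**Step 3: low-risk and high-risk groups for an assumed low-risk share f.** Low-risk cases = 40f. High-risk cases = 100 − 40f, among 20,000(1 − f) babies. This takes the high-risk group to be everyone outside the 2 per 1000 subgroup, which is also an assumption, because 6.1 and 6.3 define the risk split in different words.

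| f | Low-risk cases | Power against 52% | High-risk cases | High-risk value excluded with 80% power |
|---|---|---|---|---|
| 98% | 39.2 | 79.9% | 60.8 | about 57% |
| 95% | 38 | 78.5% | 62 | about 57% |
| 90% | 36 | 76.0% | 64 | about 58% |
| 80% | 32 | 70.3% | 68 | about 58% |
| 70% | 28 | 63.8% | 72 | about 59% |

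**Step 4: timing strata at 5 per 1000.** The protocol gives no timing cut-points, so equal splits are an assumption.

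| Stratum | Cases | Power against 61% | Value excluded with 80% power |
|---|---|---|---|
| Half (10,000) | 50 | 49% | about 55% |
| Third (about 6,667) | about 33 | 33% | about 50% |

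A higher prevalence does not rescue this. At the 6 per 1000 that 6.1 cites from a review of prevalence studies, a half has 57% power against 61%.

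**The case against.** The strongest reply is that 6.3 hedges the claim before and after making it. It also keeps the subgroup factors to two and plans accuracy estimates with confidence intervals for the main analysis. The sentence in 6.1 about confident subgroup analyses is conditional on prevalence above 0.5%, so it is not a claim about the planned design. Both points are right and limit the harm. But a caution about limited power and a statement that the analyses are powered contradict each other; the first does not correct the second.

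Three stronger readings are tempting, and the protocol does not support them.

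- *The low-risk power is badly wrong.* That depends on a share the protocol does not give. At 98% the loss is under one percentage point from the reproduced 80.8%, and it becomes material only at clearly lower shares.
- *The high-risk group is underpowered.* On the protocol's own prevalences it would hold more cases than the low-risk group and exclude a higher value than 52%. The fault is only that no figure is stated.
- *The study lacks promised power to compare subgroups.* Section 6.1 concerns a one-sample lower limit and promises nothing about differences. For illustration only, 75% against 55% gives about 56% power with 50 cases per group and about 26% with 20 (normal approximation, two-sided 5%). That shows what a null comparison would be worth; it does not show an error in a stated figure.

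Section 6.1 also mentions power plots for several sample sizes, including 10,000, the size of a timing half. Their results at that size are not given and are not linked to timing.

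**Conclusion.** The point holds in this form. The statement that the subgroup analyses are powered is unsupported for timing and for the high-risk group. The one subgroup figure that is given uses a denominator inconsistent with the overall prevalence.

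Timing is the substantive gap: splitting about 100 cases leaves about even odds of meeting the overall target in a half, and less in a third. The low-risk error is one of principle with a probably modest effect. The high-risk gap is an omission, not a demonstrated weakness.

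The reproduction in step 1 and the contradiction in step 2 use protocol figures only. The sizes in steps 3 and 4 rest on assumed shares and equal timing splits. The overall power statement is unaffected.

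**What to change.** In section 6.3, replace the sentence with a statement that:

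- the overall analysis is powered (80% to exclude 61% at 5 per 1000);
- the low-risk figure is restated for the expected number of such babies, with that number given;
- the high-risk figure is given for its expected number of cases;
- the timing analyses are exploratory estimates with exact 95% intervals, not powered to the overall target.

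In section 6.1, state the denominator behind the 2 per 1000 figures at each sample size, and bring the sentence about confident subgroup analyses into line with the new wording.

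The cost is a protocol text change and one short recalculation, with no change to design, sample size or data collection. The downside is that one stated figure becomes slightly less favourable.

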2.3. Test accuracy study design

A test accuracy study is different to an effectiveness study in that randomisation of subjects is not involved. An outline of the test accuracy study is shown in Figure 2. It is designed to generate a comparison of measurements obtained by index tests with those obtained by reference standards. In this way the accuracy of index tests can be estimated. A reference standard is a test that confirms or refutes the presence or absence of disease beyond reasonable doubt. Therefore it is sometimes also known as the gold standard. PO is the index test whereas the reference standard will be the identification of CHD cases up to one year through echocardiography, databases maintained by the West Midlands congenital anomaly register (CAR), regional cardiology referral unit, regional perinatal mortality survey, hospital information departments and, if necessary, READ codes of primary care trusts.

[figure not shown]

Figure 2 Flowchart of test accuracy study of PO as a screening tool for CHD in newborns

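### The secondary latent-class analysis in section 6.3 can overstate the sensitivity of PO and antenatal screening, and its echo-only data cannot reveal the dependence that would cause this

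*Protocol*

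**What the plan says.** Section 6.3 lists this under secondary analyses. It first acknowledges that when only screen positives are verified, the two strategies' true and false positive rates can be compared with each other, but neither test's absolute accuracy can be obtained. It then goes a step further and plans a latent-class analysis "to estimate the sensitivity and specificity of the PO test and the antenatal screening from the screen positive study using only echocardiography as a reference". It states that the method rests on an "assumption of independence of test errors in the diseased and non-diseased groups, which will be tested as part of the investigation". It names no test statistic, no data source for the test and no rule for acting on the result.

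The main analysis is separate. Under section 2.3, "the reference standard will be the identification of CHD cases up to one year through echocardiography", together with the anomaly register, the cardiology referral unit and other databases. Section 2.2 assigns echocardiography to PO-positive babies and follow-up to PO-negative babies. The study therefore plans to find CHD cases that both PO and antenatal screening missed.

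**The concern.** The step from relative to absolute sensitivity is made entirely by the independence assumption. Under independence among CHD babies, PO sensitivity is simply the PO-positive share of the antenatally detected cases, and antenatal sensitivity is the antenatally detected share of the PO-positive cases. If severe lesions are easier for both tests to find, cases detected by one test are more likely to be detected by the other, and both shares are too high. The only safeguard offered is a test of the assumption. If that test is run on the same screen-positive data, it has no information on the cell that matters, the CHD babies negative on both tests. PO has a direct estimate as well. For antenatal screening, the latent-class analysis is the only place in section 6.3 that expressly promises absolute sensitivity.

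**Working it through.** **Inputs from the protocol (section 6.1).** Sample size: "the study aims to recruit a sample of 20,000 neonates". PO accuracy: "assuming that the screening strategy will have a sensitivity of 75% and a specificity of 99.5"%. Prevalence 5 per 1000, so 20,000 × 0.005 = 100 CHD cases and 19,900 babies without CHD.

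**Assumed, not in the protocol.** Antenatal sensitivity 40% or 60% (wider range 30-60%); antenatal specificity 99.5% (also tried 98% and 99.9%); within-CHD correlation φ of 0.2 (wider range 0.15-0.30); no dependence among babies without CHD; 5% test level; echocardiography in every baby positive on either test. Section 4.3.1 names only low PO and clinical findings as triggers for echocardiography, so the last item is itself an assumption for babies who are antenatally positive and PO negative.

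**Step 1: the plan's own figure.** The protocol says "a sample size of 20,000 will have 80% power to demonstrate that sensitivity is above 61% at a prevalence of 5 per 1000". Simulating a random number of cases with exact binomial limits gives 82.5%, and 80.9% for the companion 52% figure at 2 per 1000. The stated power is reproduced closely. The protocol gives no figure for the latent-class analysis.

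**Step 2: what the data can identify.** With babies negative on both tests unverified, there are 7 observable cells: 3 with CHD, 3 without, and 1 pooled double-negative cell. That is 6 free counts. The model has 5 parameters (prevalence, two sensitivities, two specificities), which leaves 1 degree of freedom.

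**Step 3: bias.** The covariance among CHD babies is c = φ√[Se₁(1−Se₁)Se₂(1−Se₂)] = 0.2 × √(0.75 × 0.25 × 0.6 × 0.4) = 0.0424, the same for antenatal sensitivity 40% or 60%. Expected counts per 100 CHD cases:

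| | Antenatal 60% | Antenatal 40% |
|---|---|---|
| Both positive | 45 + 4.24 = 49.24 | 30 + 4.24 = 34.24 |
| PO only | 30 − 4.24 = 25.76 | 45 − 4.24 = 40.76 |
| Antenatal only | 15 − 4.24 = 10.76 | 10 − 4.24 = 5.76 |
| Both negative, true | 10 + 4.24 = 14.24 | 15 + 4.24 = 19.24 |
| Both negative, as the model infers (PO only × antenatal only ÷ both) | 5.63 | 6.86 |
| PO sensitivity, model | 49.24/60 = 82.1% | 34.24/40 = 85.6% |
| Antenatal sensitivity, model | 49.24/75 = 65.7% | 34.24/75 = 45.7% |

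In general the bias is c/Se(antenatal) for PO, here +7.1 or +10.6 points, and c/Se(PO) for antenatal screening, here +5.7. Simulated means for PO were 82.0% and 85.7%. Over φ 0.15-0.30 and antenatal sensitivity 30-60%, PO is overstated by 5.3 to 19.8 points and antenatal screening by 4.0 to 8.7. Negative c gives understatement.

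As a scale for φ only: a 50:50 lesion mix with PO sensitivity 95%/55% and antenatal sensitivity 80%/40% has c = 0.20 × 0.20 = 0.04 and φ = 0.04/0.2121 = 0.19.

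**Step 4: why the spare degree of freedom is blind.** Expected double false positives are 19,900 × 0.005 × 0.005 = 0.50, and single false positives are about 99 per test. The non-CHD double negatives implied by independence are about 99 × 99 divided by the double false-positive count: roughly 9,801 if that count is 1 and 4,900 if it is 2, against an expected 19,900 × 0.995² = 19,701. An excess of 14.24 − 5.63 = 8.6 or 19.24 − 6.86 = 12.4 CHD babies in the pooled cell cannot show against that.

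Simulation agrees. At specificity 99.5% the likelihood-ratio test rejects in 1.1-2.0% of runs with dependence and 1.9-2.0% without. The Pearson version rejects in about 6-8% either way. At antenatal specificity 98% or 99.9% the rates change but again hardly differ between dependence and independence (likelihood ratio 9.8% against 11.3%, and 0.6% against 1.1%). The same test rejects 99.8% of the time for a correlation of 0.1 confined to babies without CHD, which leaves PO sensitivity unbiased.

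**Step 5: the test with follow-up added.** On the 2×2 table of about 100 CHD cases, Fisher's test has power 46-47% at φ = 0.2 and 81-87% at φ = 0.3 (antenatal sensitivity 60% and 40%). Adding the uncorrected chi-squared test and antenatal sensitivity down to 30% gives 46-55% and 82-94%.

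**The case against.** The best case for the plan has four parts.

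First, the protocol does not say which test it will use. The phrase "from the screen positive study using only echocardiography as a reference standard" describes the estimate; it need not limit the data used for the check. A reader might infer that the planned test almost never detects dependence. That holds only for a fit test on the echo-only data. With follow-up cases the check has useful power at larger correlations. This stands, and it is a reason to keep the check and name its data.

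Second, a reader might infer that an inflated sensitivity would be accepted and drive the conclusion. Nothing in the text says that a non-significant result licenses the estimate. The analysis is secondary, the assumption is disclosed, and PO sensitivity is estimated directly in the main analysis. This also stands and limits the consequence.

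Third, the size of the bias rests on a correlation and an antenatal sensitivity that the protocol does not give. That is right: 7-11 points is an illustration, and the lesion mix above is hypothetical. Two further readings go too far. The 2 per 1000 prevalence belongs to women not selectively screened antenatally, so it is the wrong population for comparing PO with antenatal screening. The 61% criterion in section 6.1 is not attached to the latent-class estimate.

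Fourth, the direct estimate depends on complete follow-up. Section 4.4 expects no more than 5% of late-presenting cases to be missed. Read generously as 5 of 100 CHD cases, all PO negative, the direct PO sensitivity would be 75/95 = 78.9%, or 3.9 points high. That is a real limitation, but its cause is observable in part and the protocol plans to monitor it.

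What remains is that section 6.3 fixes the method and the data for the estimate, and on those data the assumption that carries the result cannot be checked where it matters.

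**Conclusion.** The point holds in a limited form. On echo-verified screen positives alone, dependence between PO and antenatal screening among CHD babies is undetectable, and this did not depend on the antenatal accuracy assumed within the range tried. The direction and size of the resulting bias do depend on assumptions: about 7-11 points for PO and about 6 for antenatal screening at correlation 0.2 and antenatal sensitivity 40-60%; about 4-20 points over the wider range; the opposite sign for negative dependence. Using follow-up cases for the test helps, but at correlation 0.2 it would still miss dependence about half the time. The primary direct estimate of PO sensitivity is untouched. The change is worth making because the study already plans to collect what is needed to avoid the assumption.

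**What to change.** In section 6.3:

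- State that sensitivity and specificity of both PO and antenatal screening will be estimated directly, taking CHD cases negative on both tests from the one-year follow-up.
- Keep the latent-class model only as a sensitivity analysis over a stated range of within-CHD correlation (for example 0 to 0.3, with negative values if thought plausible), reported beside the predicted and observed numbers of double-negative CHD cases.
- Keep the independence check, but run it on CHD cases that include those found at follow-up, and state that a non-significant result will not be taken as proof of independence.

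The cost is a few sentences and a few extra lines of analysis on data already planned. The small downside is that the latent-class result becomes a range rather than one figure.
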